## 2. VERSION HISTORY

Version	Date	Author	Comment / changes
0.1	25/10/2022	[REDACTED]	Initial draft version (based on protocol version 2.0, dated 11/08/2022)
0.2	08/03/2023	[REDACTED]	Comments from RGnCON
1.0	05/05/2023	[REDACTED]	First approved and signed version (based on protocol version 2.0, dated 11/08/2022)
1.1	31/07/2023	[REDACTED]	Draft version after data review
2.0	03/08/2023	[REDACTED]	Second approved and signed version (based on protocol version 2.0, dated 11/08/2022)

### 3. ABBREVIATIONS

List all abbreviations used in the SAP.

Abbreviation	Description
AE	Adverse event
ATC	Anatomical Therapeutic Chemical
BMI	Body mass index
CI	Confidence interval
eCRF	Electronic case report form
FAS	Full analysis set
MedDRA	Medical Dictionary for Regulatory Activities
MD	Missing data
Q1	First quartile
Q3	Third quartile
SADE	Serious Adverse Device Effect
SAE	Serious adverse event
SAP	Statistical analysis plan
SCR	Screened set
SD	Standard deviation
SOC	System organ class
WHO-DD	World Health Organization drug dictionary

## 4. PROTOCOL

Please refer to protocol version 2 dated of 11/08/2022 for the overall study design, plan description, study objectives, inclusion and exclusion criteria and sample size calculation.

## 5. ANALYSIS SETS AND SUBGROUPS

The analysis sets are defined below.

- **Screened set (SCR):** The SCR population consists of all patients who provided a written informed consent.
- **Full Analysis Set (FAS):** All patients of SCR population who have been treated at least once with RGn550 device.

Note : Patients will be analyzed as treated, i.e. according to the device actually used (either RGn550 5Hz or RGn550 10Hz). It is not planned to provide statistical analysis as randomized. If any, potential randomization errors (for example, patients who would be randomized to RGn550 5Hz but received RGn550 10Hz) will be listed.

The following subgroups will also be defined :

- **Measure of the Near Point of Convergence (NPC) at D0 before treatment :** NPC > 5
- **Maddox rod horizontal at D0 before treatment :** Horizontal deviation
- **Maddox rod vertical – Left eye at D0 before treatment :** Vertical deviation
- **Maddox rod vertical – Right eye at D0 before treatment :** Vertical deviation
- **Maddox rod vertical – Both eyes at D0 before treatment :** Vertical deviation on at least one eye.
- **Number of previous concussions :** <3 concussions vs ≥3 concussions

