9.2.3. Justification of the Clinical Investigation Design

RGnCON is a prospective, comparative, randomized, simple-blinded, monocentric, pilot clinical investigation:

- A **prospective** design has been chosen since no data on the use of RGn550 in sportspeople suffering from acute concussion syndrome were previously collected.
- This investigation is **comparative**. It involves two parallel groups differing in terms of treatment frequency: half of the patients will be treated with 5 Hz, the other half with 10 Hz. This will allow to determine which frequency is optimal for the patient both in terms of safety and performance.
- Patients will be assigned to one of these two groups through **randomization** (1:1 ratio).
- Patients will not be aware of the group they were assigned to (**simple blinded**).
- A **monocentric** design has been chosen because RGnCON is a pilot investigation.

Various methodological aspects will prevent investigation bias:

- The presence of two groups will allow to take into consideration all confounding factors, apart from placebo effect.
- The unpredictable randomization will spread all known and unknown confounding factors (apart from placebo effect) within the two groups, resulting in comparable groups, and will prevent selection bias.

- Patients will be stratified based on gender (male/female) and concussion history (history/no history of concussion within 6 months prior to inclusion) as such parameters are known to influence current concussion symptoms and complications.
- The analysis will be performed in the Full Analysis Set (FAS) population without methods to replace missing data. However, some of the used models take into consideration missing data.

Of note, the following bias will remain present:

- The follow-up bias and evaluation bias since investigators will not be blinded
- The site effect since only one site will be recruited.

Nevertheless, the primary purpose of this investigation is to evaluate, for the first time, the safety of RGn550 in sportspeople suffering from acute concussion syndrome and explore its performance in this population. In case this investigation demonstrates RGn550's safety in this population, further investigation(s), using a double-blinding design versus sham, and involving more sites, will be conducted to demonstrate RGn550's safety and performance.

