Following this, the patient will evaluate his/her symptoms using the **SCAT5 symptom evaluation tool**. The patient will rate the intensity of every symptom from 0 (none) to 6 (severe) using a form. This will allow to calculate the total number of symptoms (out of 22) and the symptom severity score (out of 132) (see Appendix 12.3).

A **blood sample** will also be obtained from the patients by a nurse. The blood sample analysis will be performed by Montpellier Neuroscience Institute (*Institut de Neuroscience de Montpellier*) following the institute standard practice.

During the visit, the patients will be **randomized** in a 1:1 ratio to the 5 Hz group or 10 Hz group using the centralized Interactive Web Response System (IWRS) incorporated into the eCRF. A block randomization method will be used. Only patients will be blinded to their assigned treatment.

Depending on their assigned group, the patients will then be **treated** with one of the 5 Hz RGn550 devices or one of the 10 Hz RGn550 devices for 20 min. To perform the treatment, the principal investigator will follow the below instructions:

- Make the patient comfortable.
- Install the helmet on the patient's head, taking care not to bump it with the modules.
- Lightly tighten the soft helmet holding wire and check the positions of the modules. Each module can be moved slightly to adjust its position.
- On the control unit, in the menu on the left, choose the option 'Program' and choose the proposed treatment
- Finally press the red arrow to start the treatment.

A countdown is displayed on the screen indicating the time remaining until the end of the treatment session. At each treatment session, the principal investigator will fulfil a treatment sheet associated with the used device and mention the number of the treated patient, date of treatment, number of

treatment session and duration of treatment. To stop the treatment, the principal investigator will press the red button with a cross inside that is displayed on the screen (a confirmation message will be displayed to avoid any manipulation error).

Following treatment, the investigators will:

- **Perform the following tests** following the methodology described above:
 - NPC
 - Cover test
 - Maddox rod test
 - Static stabilometric test
- **Collect any AEs and DDs** that occurred during the visit.

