#### 8.4.4. Adverse device events by MedDRA SOC and MedDRA PT

For all ADEs, a descriptive analysis will be provided by MedDRA SOC and MedDRA PT, by randomization arm and overall.

For all ADEs occurring during the first session (at D0), a descriptive analysis will be provided by MedDRA SOC and MedDRA PT, by randomization arm and overall.

For all ADEs occurring during the second session (at D7), a descriptive analysis will be provided by MedDRA SOC and MedDRA PT, by randomization arm and overall.

The same template as above (i.e. for Adverse events) will be used.

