## 8.5. Efficacy analysis

### 8.5.1. Analysis of the secondary performance endpoints

The secondary performance endpoints will be analyzed in the FAS population by treatment groups, excluding data that would be collected after the following intercurrent event: treatment group switch during follow-up.

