### 8.5.1.4. Blood markers

A descriptive analysis of blood markers defined in Section 0, at each time point and the change from baseline will be assessed by randomization arms and overall.

The following template will be used.

		Value at visit										Change from baseline						
		Missing	N	Mean	SD	Median	Q1	Q3	Min	Max	Mean	SD	Median	Q1	Q3	Min	Max	
RGn550 5Hz	Baseline	xx	xx	xx	xx	xx	xx	xx	xx	xx	xx	xx	xx	xx	xx	xx	xx	
	D52	xx	xx	xx	xx	xx	xx	xx	xx	xx								
RGn550 10Hz	Baseline	xx	xx	xx	xx	xx	xx	xx	xx	xx	xx	xx	xx	xx	xx	xx	xx	
	D52	xx	xx	xx	xx	xx	xx	xx	xx	xx								
Total	Baseline	xx	xx	xx	xx	xx	xx	xx	xx	xx	xx	xx	xx	xx	xx	xx	xx	
	D52	xx	xx	xx	xx	xx	xx	xx	xx	xx								

In addition, for exploratory purpose, the Blood markers will also be analyzed in the subgroup “Number of previous concussions”.

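### The randomised 5 Hz versus 10 Hz performance comparison has no as-randomised analysis, and the SAP mixes two grouping rules across its tables

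*SAP*

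**What the plan says.** **Design.** Protocol 9.5.5.1 states that "the patients will be randomized in a 1:1 ratio to the 5 Hz group or 10 Hz group". Protocol 9.2.3 gives the purpose of having two groups: "This will allow to determine which frequency is optimal for the patient both in terms of safety and performance". It relies on allocation for comparability: "The unpredictable randomization will spread all known and unknown confounding factors (apart from placebo effect) within the two groups". Only patients are blinded.

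**Grouping rule.** Protocol 9.6.2 puts all analyses in the FAS, with patients assigned as treated. SAP 5 repeats this and adds: "It is not planned to provide statistical analysis as randomized". Randomisation errors, if any, are only to be listed.

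**Performance endpoints.** SAP 8.5.1 analyses them by treatment group, "excluding data that would be collected after the following intercurrent event: treatment group switch during follow-up". SAP 8.5.1.5 plans a sensitivity analysis that keeps those data, in the same FAS, only if more than 10% of patients are excluded.

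**Other tables.** SAP 8.4.1, the primary ADE proportion, is by treatment group. For the ADE breakdown SAP 8.4.4 says: "For all ADEs, a descriptive analysis will be provided by MedDRA SOC and MedDRA PT, by randomization arm and overall". SAP 8.3 (baseline) and 8.4.3 (AEs) use the same randomisation-arm wording. The blood markers in 8.5.1.4 "will be assessed by randomization arms and overall".

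**The concern.** SAP 8.5.1.1 plans between-group differences with confidence intervals and p-values. Their protection against confounding comes from the random allocation. Grouping by device received, and discarding data after a switch, both condition on something that happens after randomisation. The principal investigator, who is unblinded, applies the treatment, so a departure from allocation related to prognosis cannot be ruled out by design. If one occurred, the planned contrast would no longer be the randomised one, and no planned performance model would recover it.

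The second issue is traceability. The primary ADE table and the ADE breakdown share the 5 Hz and 10 Hz column headings but state different grouping rules. A reader could not tell from the tables why they disagreed.

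**Working it through.** **Inputs.** N = 50 and ADE probability 0.04 (protocol 9.6.1); 1:1 allocation (protocol 9.5.5.1). I assume 25 per arm. The number of misallocated patients, k, is not given, so I use 0 to 5, all randomised to 5 Hz and treated at 10 Hz.

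**1. The plan's own figure.** 1 − 0.96^50 = 0.8701, which agrees with the stated 0.87. It depends only on the total, so the choice of grouping does not affect it.

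**2. Grouping stated, section by section.**

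| SAP section | Content | Grouping |
|---|---|---|
| 8.3 | Baseline | Randomisation arm |
| 8.4.1 | Primary ADE proportion | Treatment group |
| 8.4.3 | AEs by SOC/PT | Randomisation arm |
| 8.4.4 | ADEs by SOC/PT (all, D0, D7) | Randomisation arm |
| 8.5.1 | Performance endpoints | Treatment group |
| 8.5.1.4 | Blood markers (inside 8.5.1) | Randomisation arm |

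Protocol 9.6.3.2 has AEs by treatment group. SAP 10 lists no change of grouping and says there are no changes beyond those it lists.

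**3. ADE tables.** Expected ADE patients: 0.04 × 50 = 2. Suppose there is one in each randomised arm and the 5 Hz one was treated at 10 Hz (k = 1). Read literally, 8.4.4 shows 1/25 (4.0%) vs 1/25 (4.0%), and 8.4.1 shows 0/24 (0%) vs 2/26 (7.7%). If the misallocated patient had no ADE, the counts agree and only the denominators differ.

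**4. Performance endpoints.** Assume no true effect, and that the k misallocated patients average b SD above their arm mean. The as-treated difference is then k·b/(25 + k) + k·b/(25 − k), with standard error √(1/(25 − k) + 1/(25 + k)) in SD units for a single measurement. With b = 1:

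| k | As-treated sizes (5 Hz / 10 Hz) | False difference (SD) | Standard error (SD) |
|---|---|---|---|
| 0 | 25 / 25 | 0 | 0.283 |
| 1 | 24 / 26 | 1/26 + 1/24 = 0.08 | 0.283 |
| 3 | 22 / 28 | 3/28 + 3/22 = 0.24 | 0.285 |
| 5 | 20 / 30 | 5/30 + 5/20 = 0.42 | 0.289 |

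The false difference is proportional to b. If misallocation is unrelated to prognosis, b is zero on average and so is the bias.

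**5. What a switch removes.** There are two treatment sessions before the last assessment, so the switch that matters is at D7. For that patient the exclusion removes the D7 post-treatment and D52 oculomotor and balance values, the D14 and D52 SCAT5 scores, and the only post-baseline TMT value.

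**6. When the sensitivity analysis runs.** 5/50 = 10.0% does not exceed 10%; the first count that does is 6/50 = 12.0%. The SAP's gloss of at least 5 patients therefore conflicts with its own threshold. On either reading, one to four excluded patients trigger nothing.

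**The case against.** The strongest reply is that this is a contingency, and the trial is built to avoid it. Allocation is by central IWRS. Each patient keeps the same device, and a replacement must be of the same frequency (protocol 9.5.1, 9.5.5.2). The device used is recorded at every session. Errors will be listed, and the SAP 9 listings carry each patient's randomisation arm, so data could be regrouped. All of this stands, and it makes the likely effect small.

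As-treated grouping was also prespecified in the protocol and is conventional for safety, which is the primary endpoint. Performance is secondary and exploratory in a pilot, with a sham-controlled study to follow. That stands too, and it is why safety should stay as treated.

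An as-randomised analysis has its own cost. With k one-way misallocations, a true difference shrinks by the factor 1 − k/25: 0.96, 0.88 and 0.80 for k = 1, 3 and 5. This is a reason to keep the as-treated version alongside, not to omit the randomised one.

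Finally, the randomisation-arm wording may be loose. SAP 5 sets a general as-treated rule, and the 8.4.3 template is headed by group of treatment, like the performance template. That is plausible, but the text then needs correcting, because as written it says something else.

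A reader might infer that post-switch data are never analysed. SAP 8.5.1.5 shows otherwise, although conditionally and still as treated.

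**Conclusion.** The point holds as a gap in the plan and an inconsistency in its wording. No modelled performance analysis preserves the randomised comparison if a misallocation or switch occurs, and two grouping rules appear under the same column headings.

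The size is nil if k = 0. Otherwise it is about 0.08 SD for one patient and 0.24 SD for three, against a standard error near 0.28 SD. This assumes 25 per arm, errors all in one direction, and misallocated patients 1 SD above their arm mean.

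Two stronger readings are not supported. A reader might infer that randomisation has actually been lost; the documents report no misallocation or switch. A reader might also infer that the ADE counts in 8.4.1 and 8.4.4 will disagree. That needs a misallocated patient, an ADE in that patient, and a literal reading of 8.4.4. The 0% figure from the data review concerns loss to follow-up and does not settle the number of misallocations either way.

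**What to change.** - **Performance endpoints (SAP 5, 8.5.1):** make the main analysis by randomised arm within the FAS, using all observed data, including data after a switch. Leave the separate rule on second concussion and contraindication as it is.
- **Blood markers (8.5.1.4):** keep by randomised arm, as already written.
- **Sensitivity analysis (8.5.1.5):** make it the as-treated version with post-switch data excluded, and remove the 10% condition.
- **Safety (8.4):** keep every table as treated, replacing the randomisation-arm wording in 8.4.3 and 8.4.4. State which group a patient treated at both frequencies belongs to, which neither document does.
- **Baseline (8.3):** leave by randomised arm.
- **SAP 10:** record the departure from protocol 9.6.2, and from the post-switch exclusion in protocol 9.6.3.2. State the number of misallocations and switches; if there were none, say that the two groupings coincide.

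The cost is a SAP edit, one extra set of model runs and a documented change from the protocol. No new data are needed, and N = 50 and the 0.87 are unchanged.

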## 6. ENDPOINTS

### 6.1. Primary safety endpoint

The primary safety endpoint is the proportion of patients with at least one Adverse Device Event (ADE) after use of RGn550 in acute concussion syndrome, either at a frequency of 5 or 10 Hz.

Primary endpoint will be computed as following:

- Presence of at least one Adverse Device Event ADE (yes / no)

### 6.2. Secondary endpoints

#### 6.2.1. Secondary safety endpoints

The following secondary safety endpoints will be computed using data recorded in the “Adverse Event (AE)” Form:

- Proportion of patients with at least one mild ADE
- Proportion of patients with at least one moderate ADE
- Proportion of patients with at least one severe ADE
- Proportion of patients with at least one adverse event (AE)
- Proportion of patients with at least one device deficiencies (DDs)

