9.6.3.2. Secondary Endpoints Analysis

ADEs per severity

A descriptive analysis with 95% exact Clopper-Pearson confidence interval of mild, moderate and severe ADEs will be provided in the FAS, by treatment groups and overall.

AEs

All AEs will be described in the FAS, for each System Organ Class (SOC) and Preferred Term (PT) class using MedDRA (Medical Dictionary for Regulatory Activities) terminology, by treatment groups and overall.

DDs

All DDs will be described in the FAS, by treatment groups and overall.

| | |
|--|--------------|
| 2022.08.11_RGnCON_Prot_Final_V2.0_clean_public | Page 48 / 82 |
|--|--------------|

Secondary performance analyses

The secondary performance analyses will be performed in the FAS by treatment groups, excluding data that would be collected after the following intercurrent event: treatment group switch during follow-up.

Imputation of missing data will be handled by the mixed model (details will be provided in the Statistical Analysis Plan).

The analyses will be performed as follows:

- For the evolution of the below parameters, the following timepoints will be compared: (D0 after treatment - D0 before treatment, D7 before treatment - D0 before treatment, D7 after treatment - D0 before treatment, and D52 – D0 before treatment) and a mixed effect regression model will be used with a patient random effect. Group effects (5 Hz vs 10Hz), period effects (D0 before, D0 after, D7 before, D7 after and D52) and the group-by-period interaction will be added as fixed effects. The stratification variables will be added in the model as covariates.
 - Automated oculomotor and oculopostural functions:
 - Convergence, evaluated with the Near Point of Convergence (NPC) (>5 cm vs ≤5 cm)
 - Deviation as evaluated with the cover test (normal fixation or light restitution movement or important restitution movement or deviated eye without restitution movement)
 - Horizontal deviation as evaluated with the Maddox rod test (orthophoria or exophoria or esophoria and measure in diopter)
 - Vertical deviation of the right eye as evaluated with the Maddox rod test (orthophoria or hypophoria or hyperphoria and measure in diopter)
 - Vertical deviation of the left eye as evaluated with the Maddox rod test (orthophoria or hypophoria or hyperphoria and measure in diopter)
 - Balance function:
 - Statokinesigram area (m²)
 - Difference between left distribution and right distribution (%)

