9.13.1.6. Device Deficiency (DD)

Any inadequacy in the identity, quality, durability, reliability, safety or performance of an investigational device, including malfunction, use errors or inadequacy in information supplied by the manufacturer (*Regulation 2017/745*).

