9.13.3. Safety Reporting to Sponsor

Per Article 80 of the European Regulation 2017/745, the following events shall be recorded:

- Any AE of a type identified in the CIP as being critical to the evaluation of the results of that clinical investigation
- Any SAEs
- Any DD that might have led to a SAE if appropriate action had not been taken intervention had not occurred, or circumstances had been less fortunate
- Any new findings in relation to the above events.

The following events that occur in patients included in RGnCON from inclusion to the end of the 52-day follow-up period will thus be recorded:

- All AEs, including SAEs
- All DDs
- Any new findings in relation to AEs and DDs.

AEs will be reported using the Adverse Event form of the eCRF while DDs will be reported using the Device Deficiency form. The date of the event, its severity, causality, treatment and resolution will notably be collected.

These events will be reported immediately to REGEnLIFE and no later than 3 calendar days after the investigator becomes aware of the event.

If needed, the investigations site team or [REDACTED] can contact REGEnLIFE's materiovigilance department via email ([contact]) or phone ([contact]).

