### 8.4.2. Analysis of the secondary safety endpoints / overall summary of adverse events

For all secondary safety endpoints listed in Section 6.2.1, a descriptive analysis will be provided. Table will summarize the number and percentage of patients experiencing the event and the 95% CI. The same analysis will be performed for SAE and SADE.

All AEs collected in the eCRF will be used for the analysis.

The following template will be used.

	RGn550 5Hz N=xx	RGn550 10Hz N=xx	Total (N=XX)
Secondary safety endpoints:			
At least one AE - N (%)	xx (xx.x)	xx (xx.x)	xx (xx.x)
95% CI	xx.x ; xx.x	xx.x ; xx.x	xx.x ; xx.x
At least one ADE - N (%)	xx (xx.x)	xx (xx.x)	xx (xx.x)
95% CI	xx.x ; xx.x	xx.x ; xx.x	xx.x ; xx.x

	RGn550 5Hz N=xx	RGn550 10Hz N=xx	Total (N=XX)
At least one mild ADE - N (%)	xx (xx.x)	xx (xx.x)	xx (xx.x)
95% CI	xx.X ; xx.X	xx.X ; xx.X	xx.X ; xx.X
At least one moderate ADE - N (%)	xx (xx.x)	xx (xx.x)	xx (xx.x)
95% CI	xx.X ; xx.X	xx.X ; xx.X	xx.X ; xx.X
At least one severe ADE - N (%)	xx (xx.x)	xx (xx.x)	xx (xx.x)
95% CI	xx.X ; xx.X	xx.X ; xx.X	xx.X ; xx.X
At least one DD - N (%)	xx (xx.x)	xx (xx.x)	xx (xx.x)
95% CI	xx.X ; xx.X	xx.X ; xx.X	xx.X ; xx.X
Other categories of AEs:			
At least one SAE - N (%)	xx (xx.x)	xx (xx.x)	xx (xx.x)
95% CI	xx.X ; xx.X	xx.X ; xx.X	xx.X ; xx.X
At least one SADE - N (%)	xx (xx.x)	xx (xx.x)	xx (xx.x)
95% CI	xx.X ; xx.X	xx.X ; xx.X	xx.X ; xx.X

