## 10. CHANGES IN THE STATISTICAL METHODS FROM THOSE STATED IN THE PROTOCOL

This SAP is based on protocol version 2.0 and CRF version 2.0.

Changes in the statistical methods compared with those stated in the protocol are the following.

Add analysis subgroups:

- Subgroups analysis (“NPC > 5 at D0 before treatment”, “Horizontal deviation at D0 before treatment”, “Vertical deviation at D0 before treatment” (Maddox rod vertical – Left eye) and “Vertical deviation on at least one eye at D0 before treatment” (Maddox rod vertical – Both eyes), “number of previous concussions”).

Add secondary endpoints:

- Rombert quotient and Statokinetic distribution index calculation.

Add analysis of:

- NPC measurement in the subgroup “NPC > 5 at D0 before treatment”.
- Maddox rod horizontal score in the subgroup “Horizontal deviation at D0 before treatment”.
- Maddox rod vertical left eye in the subgroup “Vertical deviation at D0 before treatment”
- Maddox rod vertical both eyes in the subgroup “Vertical deviation at least one eye at D0 before treatment”.

Add descriptive analysis of ADE occurring during the first session (D0) and during the second session (at D7).

Add Exploratory analyses: study of potential relationship between drowsiness and concussion severity parameters.

There were no other changes in the statistical methods from those stated in the protocol.

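### SAP 6.2.1 reads the device-deficiency endpoint from the Adverse Event form, but the protocol records deficiencies on a separate form; a minor correction to one descriptive endpoint

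*SAP*

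**What the plan says.** SAP 6.2.1 introduces its list with a single source rule: "The following secondary safety endpoints will be computed using data recorded in the" Adverse Event form. Five endpoints follow: mild, moderate and severe adverse device effects (ADEs), any AE, and any DD. The DD bullet has no source of its own.

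SAP 8.4.2 gives the analysis. Its table has a row labelled "At least one DD - N" (%), with a 95% confidence interval, by group and overall. The only statement there about input data is "All AEs collected in the eCRF will be used for the analysis".

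Protocol 9.13.3 describes the recording: "AEs will be reported using the Adverse Event form of the eCRF while DDs will be reported using the Device Deficiency form". Protocol 9.6.3.2 sets the intended analysis: "All DDs will be described in the FAS, by treatment groups and overall".

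**The concern.** The SAP points the DD endpoint at a form where, according to the protocol, DDs are not entered. A device fault that harms nobody would go on the Device Deficiency form and leave nothing on the Adverse Event form. A program that followed the SAP would not count it.

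DD incidence is a stated secondary objective and endpoint (Protocol 9.4.2 and 9.5.4.2), in what Protocol 9.2.3 describes as the first safety evaluation of RGn550 in this population. The protocol also expects that faults can happen: section 9.5.1 supplies a second device of each type, which may be used for a given patient only if the first malfunctions. An understated DD row would make the device look more reliable in the summary table than the records show.

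**Working it through.** This is mainly a comparison of texts. The arithmetic only illustrates the consequence.

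**1. Where DDs are entered.** Protocol 9.13.3 names two eCRF forms, one for AEs and one for DDs.

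**2. Where the SAP looks.** SAP 6.2.1 names the Adverse Event form for all five endpoints. SAP 8.4.2 names AEs only.

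**3. Whether a DD can exist without an AE.** Protocol 9.13.1.6 defines a DD as "Any inadequacy in the identity, quality, durability, reliability, safety or performance of an investigational device", and includes malfunctions, use errors and inadequate manufacturer information. No medical event is required. Protocol 9.13.1.1 defines an AE by a medical occurrence, disease, injury or clinical sign. So a DD need not produce an AE record. Where a DD does lead to an AE, nothing in the documents says that the Adverse Event form marks the event as a DD.

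**4. Whether other SAP text repairs the rule.**
- The notes in 6.2.1 define coding, ADEs and the timing of ADEs by session. They give no DD derivation.
- Section 9 lists every eCRF form, but as listings and not as an endpoint source.
- Section 10 declares no change of DD source and closes with "There were no other changes in the statistical methods from those stated in the protocol".
- No section names the Device Deficiency form.

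**5. Size.** The plan states no DD figure. Its one sample-size figure, a 0.87 probability of seeing at least one ADE (Protocol 9.6.1), reproduces as 1 − 0.96^50 = 0.8701. It concerns ADEs, and this point does not depend on it.

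For illustration, take the planned n = 50 and assumed numbers x of patients with a DD. The exact Clopper-Pearson limits are the 0.025 quantile of Beta(x, n − x + 1) and the 0.975 quantile of Beta(x + 1, n − x). For x = 0 the upper limit is 1 − 0.025^(1/n).

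| Patients with a DD (assumed) | Device Deficiency form as source | Adverse Event form as source, if it identifies none of them |
|---|---|---|
| 1 | 2.0% (0.1 to 10.6) | 0/50 (0 to 7.1) |
| 2 | 4.0% (0.5 to 13.7) | 0/50 (0 to 7.1) |
| 3 | 6.0% (1.3 to 16.5) | 0/50 (0 to 7.1) |
| 5 | 10.0% (3.3 to 21.8) | 0/50 (0 to 7.1) |

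Here 1 − 0.025^(1/50) = 0.0711. For one group of 25, assuming equal groups, 1 − 0.025^(1/25) = 0.1372, so 0/25 has an upper limit of 13.7%. These limits belong to any zero count at these sizes. They do not measure the error.

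**The case against.** The strongest reply is that the intention is plain and the damage limited. Protocol 9.6.3.2 wants every DD described, SAP 8.4.2 keeps a DD row, and section 10 announces no departure. The opening sentence of 6.2.1 looks like a drafting slip that fits four of its five bullets. A programmer who found no DD field on the Adverse Event form would probably ask before reporting zero. SAP section 11 also has validation outputs reviewed by a third party.

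Much of this stands, and it sets the grade of the point. It does not remove the conflict. The SAP's written rule and the protocol's recording rule disagree, and a reviewer checking against the SAP could pass the wrong source. The text is also in the second signed SAP, issued after data review.

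Two stronger readings are tempting, and the documents support neither.

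- A reader might infer that the deficiencies are lost. They are not. SAP section 9 provides a tab for each eCRF form with analysis set and arm added, so a wrong zero could be seen against the listing. Protocol 9.13.3 sends DDs to the sponsor within 3 calendar days, so safety oversight during the trial does not rest on this table.
- A reader might infer that the DD row must come out as 0/50 whatever happened. That assumes the Adverse Event form identifies no DD. The SAP is based on CRF version 2.0, which is not among the documents, so this cannot be checked.

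**Conclusion.** The point holds as an inconsistency between the SAP and the protocol over a data source. Applied literally, SAP 6.2.1 and 8.4.2 would leave out of the DD row, and of its confidence interval, any DD entered only on the Device Deficiency form. The direction of the error is understatement. Its size is unknown, since no DD rate is given and 50 is the planned number rather than the actual analysis set.

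The conclusion rests on the two documents describing the eCRF correctly. If the Adverse Event form also captures DDs, the effect is smaller. The point is minor: it touches one descriptive secondary endpoint with no hypothesis test, and leaves the primary endpoint, alpha and sample size as they are.

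**What to change.** Make two short edits to the SAP.

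- **Section 6.2.1:** limit the Adverse Event form sentence to the AE and ADE endpoints. Add that the DD endpoint is computed from the Device Deficiency form, with records assigned to patients by the patient's eCRF identifier.
- **Section 8.4.2:** state that the AE, ADE, SAE and SADE rows use all AEs in the eCRF, and that the DD row uses all records on the Device Deficiency form.

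The patient identifier is the right key because Protocol 9.7 identifies patients in the eCRF by a numeric identifier. The device label would not do: Protocol 9.5.1 provides four devices, which is 50 / 4 = 12.5 patients per device on average, so a label alone cannot single out a patient or a session.

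The edits bring the SAP back to the protocol, so section 10 needs no new entry. They use data the protocol already requires, and the cost is a few lines of text and the source of one table row.
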